9.3.2 Pharmacokinetic Statistical Methodology

The PK parameter estimates will be evaluated to determine the impact of age on the PK of lasmiditan and its metabolites. Log-transformed C_{\max} and $AUC(0-\infty)$ will be evaluated in a linear fixed-effects model with a fixed effect of age group (elderly, young). The 90% confidence intervals (CIs) of the ratios of geometric means of the elderly group versus the young group will be presented. An example of the SAS code that will be used is as follows:

```
proc mixed data=xxx;  
class agegroup;  
model l_pk = agegroup / alpha=0.1;  
lsmeans agegroup / pdiff;  
run;
```

where l_pk is the log-transformed (base e) PK parameter.

The t_{\max} will be analyzed using a Wilcoxon rank sum test. Estimates of the median difference between elderly and young subjects based on the observed medians, 90% CIs and the p-value from the Wilcoxon test will be calculated.

Additional analysis will be performed if warranted upon review of the data.

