4.2 Secondary objectives

- To compare the PK of lasmiditan in healthy elderly subjects (≥ 65 years of age) against the PK of lasmiditan in healthy young subjects (18 to 45 years of age) following a single 200 mg oral dose of lasmiditan.
- To assess the safety and tolerability of a single 200 mg oral dose of lasmiditan in elderly and young healthy subjects.

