7. SAMPLE SIZE JUSTIFICATION

Up to 36 subjects may be enrolled in order that 30 subjects (2 groups of 15) complete the study. For area under the curve (AUC) or maximum observed drug concentration (C_{max}), assuming inter-subject coefficient of variation (CV) of 40% and a sample size of 15 per group, the 90% confidence interval around the ratio of the geometric means (elderly group : non-elderly group) will have half-width of 24.3% on the log scale with 90% coverage probability.

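### Does the misplaced alpha option in the example SAS code endanger the promised 90% interval for the elderly-to-young ratio?

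*SAP*

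**What the plan says.** Section 9.3.2 of the SAP specifies the age comparison in prose and then illustrates it in code.

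- **Prose.** Log-transformed Cmax and AUC(0-∞) are to be "evaluated in a linear fixed-effects model with a fixed effect of age group (elderly, young"). The reported result is stated directly: "The 90% confidence intervals (CIs) of the ratios of geometric means of the elderly group versus the young group will be presented". The log is base e.
- **Code.** It is introduced with "An example of the SAS code that will be used is as follows". It opens with "proc mixed data=xxx", a placeholder dataset name, and then has "model l_pk = agegroup / alpha=0.1" and "lsmeans agegroup / pdiff". There is no `CL` option, no `ALPHA=` on the PROC or LSMEANS statement, and no ESTIMATE statement.

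Two other places bear on the point. Section 4.2 makes the age comparison a secondary objective ("To compare the PK of lasmiditan in healthy elderly subjects"). Section 7 justifies the sample size by the precision of "the 90% confidence interval around the ratio of the geometric means (elderly group : non-elderly group").

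**The concern.** The code and the sentence before it do not match. In PROC MIXED, `ALPHA=` on the MODEL statement governs confidence limits for the fixed-effect parameters, and the example does not request those. It does not carry over to LSMEANS. With `PDIFF` alone, LSMEANS prints the difference, its standard error, degrees of freedom, t statistic and p-value, but no limits. The code therefore yields a p-value for which the SAP plans no use with Cmax and AUC(0-∞), and omits the interval that it does plan to report. It also stops at the log scale, with no step back to a ratio.

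What would be at stake is the main output of a secondary objective, and the interval on which the sample size rests. The slip also has a plausible follow-on error. A programmer who notices the missing limits and adds only `CL` to LSMEANS would get the default 95% level, while the visible `alpha=0.1` suggests 90%. One template could serve lasmiditan and three metabolites for two parameters each, so such an error could recur in up to 4 × 2 = 8 fits.

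**Working it through.** **1. What the prose fixes, set against what the code supplies.**

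| Element | Prose of the SAP | Example code |
|---|---|---|
| Scale | natural log (9.3.2) | `l_pk` |
| Model | one fixed effect, age group (9.3.2) | same |
| Contrast | elderly versus young (9.3.2; same direction in 7) | difference of LS means; Elderly sorts before Young under the names in Section 6, so the direction agrees |
| Level | 90% (9.3.2 and 7) | 0.1 appears, but on MODEL |
| Limits | to be presented (9.3.2) | not requested |
| Reported quantity | ratio of geometric means (9.3.2) | log difference only |

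With a single two-level factor, the prose determines the interval uniquely. For an estimated log difference d with standard error SE and residual degrees of freedom df, it is exp(d ± t(0.95, df) × SE). The code as written prints d, SE and df.

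**2. The plan's own precision figure.** Inputs from Section 7: CV 40%, 15 per group, 90% interval, stated half-width 24.3% on the log scale.

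- SD on the log scale: √ln(1 + 0.40²) = 0.3853
- SE of the difference: 0.3853 × √(2/15) = 0.1407
- df = 2 × 15 − 2 = 28, and t(0.95, 28) = 1.7011
- Half-width: 1.7011 × 0.1407 = 0.2393, or 23.9%

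This is close to 24.3% but not equal to it. The normal quantile gives 23.1%; taking the SD as 0.40 gives 24.0% (normal) or 24.8% (t). None of these gives 24.3% exactly. The sample size still agrees: 15 per group is the smallest number with a t-based half-width at or below 24.3%, since 14 per group gives 24.8%. The small gap has no bearing on where the option sits in the code.

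**3. The interval recovered from the printed output.** With SE = 0.1407, df = 28 and an observed ratio of 1.00 (d = 0), the 90% limits are exp(±0.2393) = 0.787 to 1.270.

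**4. The hypothetical edit (`CL` added to LSMEANS without `ALPHA=`).**

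- t(0.975, 28) = 2.0484
- Half-width: 2.0484 × 0.1407 = 0.2882
- Limits at an observed ratio of 1.00: exp(±0.2882) = 0.750 to 1.334
- Ratio of half-widths: 0.2882 / 0.2393 = 1.204

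With 18 per group (all 36 subjects enrolled, df = 34), the half-widths are 0.2610 and 0.2171, a ratio of 1.202.

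Step 4 describes an edit that the SAP does not contain. The effect of the text as it stands on any reported number is nil.

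**The case for a change.** The best argument for amending the SAP is that the snippet is presented as an example of what will actually be run, and that Section 3 makes the finalized SAP and table shells the template for the study report. Its one interval-related option has no effect on the contrast of interest. Correcting it would take two option edits and perhaps a sentence on exponentiation, with no downside. A visible 0.1 on the wrong statement could also mislead someone working quickly.

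The factual part of this stands: the option is misplaced and `CL` is missing. The inference that the plan needs changing does not follow. The snippet has a placeholder dataset and no output steps, so it sketches the model and is not a finished program. A programmer who runs it will see at once that the required limits are absent, and the preceding sentence gives the level to use. For 95% limits to reach the report, someone would have to add `CL`, omit the level, and have the result pass checking against text that says 90% in two sections. The missing back-transformation adds nothing, because a ratio of geometric means from a natural-log model is by definition the exponentiated difference.

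**Conclusion.** This is a clerical slip in illustrative code, and no change to the plan follows. An analyst following Section 9.3.2 would report the correct 90% interval, either by requesting it on LSMEANS or by computing it from the printed estimate, standard error and degrees of freedom. No estimate, sample size or conclusion depends on the snippet, and the SAP attaches no test or equivalence margin to this interval. The figure of 1.20 times the intended width measures only a possible later programming error that would contradict the text.

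The conclusion assumes standard PROC MIXED option behaviour, which was not confirmed by running SAS. If the MODEL option did carry over to LSMEANS, the point would be weaker still. The half-widths assume the Section 7 inputs of CV 40% and 15 per group.

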11. CHANGES FROM THE PROTOCOL SPECIFIED STATISTICAL ANALYSES

Since the data will not be paired due to the study design, Wilcoxon rank sum test will be used for the analysis of t_{\max} instead of the Wilcoxon signed rank test that was stated in the protocol.

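### For tmax the SAP fixes the estimate as a difference of observed medians beside a Wilcoxon rank sum test, and does not say clearly which procedure yields the 90% CI

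*SAP*

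**What the plan says.** Section 9.3.2 of the SAP states that tmax "will be analyzed using a Wilcoxon rank sum test". It then sets out the results to report: "Estimates of the median difference between elderly and young subjects based on the observed medians, 90% CIs and the p-value from the Wilcoxon test". The example SAS code in that section covers only the model for log-transformed Cmax and AUC, so no code shows how the tmax interval is obtained.

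Section 11 records one change from the protocol: "Since the data will not be paired due to the study design, Wilcoxon rank sum test will be used" in place of the signed rank test. It changes the test and leaves the estimate and the interval alone. Section 13.1 deals only with how values are rounded and displayed. Section 3 refers to a separate TFL shell document for detailed table descriptions, which is not available here. Section 7 plans that "30 subjects (2 groups of 15) complete the study", and its precision statement concerns AUC and Cmax, not tmax.

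**The concern.** A rank sum test can be inverted to give a confidence interval for the shift between two groups. The limits are ordered elderly-minus-young pairwise differences, and the point estimate from the same procedure is the median of those differences (Hodges-Lehmann). The difference of the two group medians is another estimator and usually another number.

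The sentence in Section 9.3.2 can be read in two ways:

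- The closing reference to the Wilcoxon test covers both the interval and the p-value. Then the printed estimate comes from one procedure and the interval beside it from another.
- It covers the p-value only. Then the interval has no named method in the SAP. A difference of medians has no single default interval, so two programmers could report different limits.

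At stake is whether the tmax row of the age comparison, which serves a secondary objective (Section 4.2), can be reproduced and is internally consistent. A less precise estimate may also be printed where a more precise one is available from the same test.

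**Working it through.** **Inputs.** From the SAP: rank sum test, difference of observed medians, 90% level (Section 9.3.2); unpaired groups (Section 11); 15 per group (Section 7); actual sampling times for individual PK parameters (Section 9.3.1). The SAP gives no tmax distribution, and no tmax figure to reproduce. Assumed: lognormal tmax, young median 2 h, log SD 0.3 to 0.6, elderly:young ratio 1 to 1.5. Times were either continuous or taken from assumed sampling grids with actual times varying by ±3 min.

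**1. The interval that belongs to the rank sum test.** With m = n = 15 there are 15 × 15 = 225 pairwise differences.

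- Large-sample position of the lower limit: mn/2 − 1.645 × √(mn(m+n+1)/12) = 112.5 − 1.645 × √(225 × 31/12) = 112.5 − 1.645 × 24.11 = 72.84, which rounds to 73.
- The exact null distribution also gives the 73rd difference. The upper limit is the (226 − 73) = 153rd. Exact coverage without ties is 90.2%.
- The matching estimate is the middle difference, the (225 + 1)/2 = 113th.

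**2. How far the two estimates differ.** With continuous times and log SD 0.4 to 0.6, they differed in about 97% of simulated trials, with a mean absolute gap of 0.14 to 0.24 h. With gridded times varying by ±3 min (three assumed grids, log SD 0.3 and 0.5), they differed by more than 0.1 h in 17-47% of trials.

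**3. Precision.** Continuous times, 20,000 trials per row:

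| Log SD | Elderly:young ratio | SD, difference of medians (h) | SD, Hodges-Lehmann (h) | Ratio of SDs |
|---|---|---|---|---|
| 0.4 | 1.0 | 0.364 | 0.296 | 1.23 |
| 0.4 | 1.3 | 0.422 | 0.345 | 1.22 |
| 0.5 | 1.0 | 0.462 | 0.367 | 1.26 |
| 0.5 | 1.3 | 0.532 | 0.429 | 1.24 |
| 0.6 | 1.0 | 0.552 | 0.432 | 1.28 |
| 0.6 | 1.3 | 0.650 | 0.511 | 1.27 |

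At log SD 0.3 and 0.5 with ratios 1, 1.25 and 1.5, the ratio of SDs was 1.197 to 1.265. With times varying by ±3 min around an assumed 0.5-8 h grid the excess was 20-31%; over three assumed grids it was 8-39%. Other shapes: normal 1.199, Laplace 0.985, t with 2 df 1.012. The gain therefore depends on the tails not being heavy.

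**4. Validity of the rank-inversion interval for the printed quantity.** It covered the true difference of medians in 89.8-90.5% of trials with continuous times and in 90.5-93.9% with gridded times varying by ±3 min. The difference of medians fell outside the interval in 0.03-0.1% and 0.1-1.2% of trials respectively.

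**5. Target when the effect is not a pure shift.** At log SD 0.5, a 1.25-fold change has a true difference of medians of 2 × 1.25 − 2 = 0.50 h. The simulated means were 0.48 h (Hodges-Lehmann) and 0.51 h (difference of medians). For a 1.5-fold change the true value is 1.00 h and the means were 0.97 and 1.02 h.

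**The case against.** The strongest reply is that the SAP never says that the interval is Wilcoxon-based. The reference to the Wilcoxon test can attach to the p-value alone, and then there is no mismatch, only a method that the TFL shells may name. This stands. A reader might infer that the SAP specifies a mismatched pair, or that the plan as a whole has no interval method. The text supports neither. It supports only that the SAP sentence is unclear and that either reading needs repair.

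A reader might also infer that the interval would be wrong for the quantity printed beside it. The coverage results contradict that: under the assumptions used, it holds about its nominal level or more for the true difference of medians.

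A third reply is that the difference of medians is transparent, can be checked against the summary table, and is aimed directly at the difference of medians, which Hodges-Lehmann is not when the age effect is multiplicative. The first two points stand, and they are why the observed medians should stay in the table. The third carries little weight. At log SD 0.5 and ratio 1.3 the true difference is 0.60 h. Hodges-Lehmann averaged 0.578 h with SD 0.429 h, so its root mean squared error is √(0.429² + 0.022²) = 0.43 h. The difference of medians averaged 0.611 h with SD 0.532 h, giving √(0.532² + 0.011²) = 0.53 h. The small bias costs far less than the extra variance.

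Finally, all the precision figures rest on an assumed distribution and assumed sampling times, and the advantage vanishes for heavy tails. That stands too.

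**Conclusion.** The point holds as a minor one. Section 9.3.2 fixes an estimate that is not the natural partner of the test it names, and leaves the source of the 90% CI unclear. The loss is one of efficiency and consistency: an SD about 20-30% larger at 15 per group if tmax is roughly lognormal with median 2 h and log SD 0.3 to 0.5, and none if the tails are heavy. It does not make the analysis invalid. The Wilcoxon p-value is the same either way, the Cmax and AUC comparisons are untouched, tmax does not enter the sample-size statement, and no decision rule in the SAP uses it. It is worth correcting because the correction is small, not because any conclusion of the trial depends on it.

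**What to change.** Replace the reporting sentence for tmax in Section 9.3.2 with:

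> The Hodges-Lehmann estimate of the elderly-minus-young shift in tmax and its rank-inversion 90% CI (PROC NPAR1WAY WILCOXON HL, alpha=0.1) will be reported with the Wilcoxon rank-sum p-value; the observed medians and their difference will be shown descriptively.

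Estimate, interval and p-value then come from one procedure. If the sponsor prefers to keep the difference of medians as the estimate, the SAP should name an interval built for it (a bootstrap interval, for example) and state that only the p-value comes from the Wilcoxon test. The TFL shells should agree with whichever is chosen.

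The cost is one sentence and one SAS option, and no information leaves the table. Exact or large-sample limits make no difference at 15 v 15, since both give the 73rd and 153rd ordered differences. The one drawback is the slightly different target when the age effect is not a pure shift, about 0.03 h in the 1.25-fold case above.

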9.4 Safety and Tolerability Assessments

9.4.1 Adverse events

Where changes in severity are recorded in the Case Report Form (CRF), each separate severity of the adverse event (AE) will be reported in the listings, only the most severe will be used in the summary tables. A pre-existing condition is defined as an AE that starts before the subject has provided written informed consent and is ongoing at consent. A non-treatment emergent AE is defined as an AE which starts after informed consent but prior to dosing. A treatment-emergent AE is defined as an AE which occurs postdose or which is present prior to dosing and becomes more severe postdose.

All AEs will be listed. Treatment-emergent AEs will be summarized by age group, treatment, severity and relationship to the study drug. The frequency (the number of adverse events, the number of subjects experiencing an adverse event and the percentage of subjects experiencing an adverse event) of treatment-emergent adverse events will be summarized by age group, treatment, Medical Dictionary for Regulatory Activities (MedDRA) version 20.0 system organ class and preferred term. The summary and frequency adverse event tables will be presented for all causalities and those considered related to the study drug. Any serious adverse events will be tabulated.

9.4.2 Concomitant medication

Concomitant medication will be coded using the WHO drug dictionary (Version September 2016 Enhanced Dictionary B2 Format). Concomitant medication will be listed.

9.4.3 Clinical laboratory parameters

All clinical chemistry, hematology and urinalysis data will be listed. Additionally clinical chemistry, hematology and urinalysis data outside the reference ranges will be listed.

Values for any clinical chemistry, hematology and urinalysis values outside the reference ranges will be flagged on the individual subject data listings.

9.4.4 Hepatic Monitoring

If a subject experiences elevated alanine aminotransferase (ALT) $\geq 3 \times$ upper limit of normal (ULN), alkaline phosphatase (ALP) $\geq 2 \times$ ULN, or elevated total bilirubin (TBL) $\geq 2 \times$ ULN, liver tests will be performed to confirm the abnormality.

The subjects' liver disease history and associated person liver disease history data will be listed. Any concomitant medication of acetaminophen/paracetamol will be listed. Results from any

hepatic monitoring procedures, such as a magnetic resonance elastography (MRE) scan and a biopsy assessment will be listed, if performed.

Hepatic risk factor assessment data will be listed. Liver related signs and symptoms data will be summarized by age group and treatment, and listed, if available.

All hepatic chemistry, hematology, coagulation, and serology data will be summarized by parameter, age group, and treatment, and listed. Values outside the reference ranges will be flagged on the individual subject data listings.

9.4.5 Vital signs

Where supine (or semi-recumbent for elderly subjects) blood pressure and pulse rate are measured in triplicate, the mean value will be calculated and used in all subsequent calculations. When triplicate blood pressure or pulse rate measurements precede a standing measurement, the last supine (or semi-recumbent for elderly subjects) blood pressure or pulse rate measurement will be used for orthostatic calculations. Orthostatic changes will be calculated as the standing value, minus the last supine (or semi-recumbent for elderly subjects) value taken prior to the standing value.

Vital signs data will be summarized by age group and treatment together with changes from baseline, where baseline is defined as the mean of the triplicate measurement on Day 1 predose of each treatment period for supine (or semi-recumbent for elderly subjects) vital signs, and the last measurement on Day 1 predose of each treatment period for standing and orthostatic vital signs. Figures of mean vital signs and mean changes from baseline profiles by treatment will be presented by age group and treatment over time. Furthermore, values for individual subjects will be listed.

Changes from baseline will be calculated for vitals signs. Changes from baseline of >30 mmHg for systolic blood pressure and of >20 mmHg for diastolic blood pressure are considered to be of potential clinical concern and will be highlighted on the individual changes from baseline data listings. Orthostatic decreases of >20 mmHg for systolic and diastolic blood pressure or an increase in heart rate of >20 bpm are considered to be of potential clinical concern, and will also be highlighted on the individual data listings.

9.4.6 Electrocardiogram (ECG)

For each subject, ECGs will be performed for safety purposes only, and will not be reported.

9.4.7 Other assessments

All other safety assessments not detailed in this section will be listed but not summarized or statistically analyzed.

9.4.8 Safety and Tolerability Statistical Methodology

No inferential statistical analyses are planned.

10. INTERIM ANALYSES

No interim statistical analyses are planned.

11. CHANGES FROM THE PROTOCOL SPECIFIED STATISTICAL ANALYSES

Since the data will not be paired due to the study design, Wilcoxon rank sum test will be used for the analysis of t_{\max} instead of the Wilcoxon signed rank test that was stated in the protocol.

13. DATA PRESENTATION

13.1 Derived Parameters

Individual derived parameters (e.g. PK parameters) and appropriate summary statistics will be reported to three significant figures. Observed concentration data, e.g. C_{\max} , should be reported as received. Observed time data, e.g. t_{\max} , should be reported as received. N and percentage values should be reported as whole numbers. Median values should be treated as an observed parameter and reported to the same number of decimal places as minimum and maximum values.

13.2 Missing Data

Missing data will not be displayed in listings.

